11. STATISTICS AND ANALYSIS

11.1. The Number of Participants

The PiLOT-AF study aims to give some insights about the relation among RF power, LSI and incidence of oesophageal temperature alerts during AF ablation on the LA posterior wall. In view of the absence of data on this topic, it has been designed as pilot study for power analysis and sample size calculation of a further main study.

As suggested before for pilot studies (38), we aim to a final sample size of 12 patients with primary outcome data per each treatment group. We know from previous studies that oesophageal temperature alerts occur in 55-75% of AF ablations. Therefore, if taking into account also participants who do not experience oesophageal temperature alerts during AF ablation, we plan to recruit a total of 80 patients in order to achieve primary outcome data in 12 patients per group.

11.2. Description of Statistical Methods

Comparison of primary, secondary and tertiary outcome measures among different treatment groups will be performed at each time point using appropriate statistical testing. In particular, ANOVA tests will be used to compare numerical variables and chi-square tests will be used to compare categorical values.

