3.4 Research questions

On these premises, our research questions are:

- is it better to use higher RF powers for shorter times, than lower RF powers for longer times, to reduce the risk of oesophagus overheating and oesophageal temperature alerts?
- is the suggested LSI value of 5 on the LA posterior wall feasible or thwarted by frequent occurrence of temperature alerts leading to premature termination of RF delivery, regardless of maximum power?
- what is the impact of the different RF energy settings on PVI, acute pulmonary vein reconnection (PVR) and short-term clinical success of the AF procedure?
- which LSI value and RF power should be used during RF ablation on the LA posterior wall in order to achieve the best compromise between safety from oesophageal damage and lesion transmuralty and durability?

To these aims, the PiLOT-AF study aims to test different combinations of RF power and LSI during PV encirclement on LA posterior wall.

The rate of oesophageal alerts will be collected and compared for each procedure modality. The rate of first pass PVI and acute PVR (related to breakthrough signals on LA posterior wall), the procedure duration and RF ablation time will be also collected as clinical indicators of lesion transmuralty and acute procedure success. The freedom from AF at 6 months follow-up will be used as clinical indicators of lesion durability and short-term procedure success. The occurrence of any oesophageal symptoms at follow-up will be recorded as surrogate clinical indicators of oesophageal damage. All other procedural complications will be also recorded as safety outcomes.

No data are currently available on this topic. Therefore, this study has been designed as pilot study for power analysis and sample size calculation of a further main study.

This pilot study will hopefully give us some insights about the best combination of RF power, application time and target LSI to use during AF ablation on the LA posterior wall in order to achieve durable PVI with minimal risks of oesophageal damage.

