11.3. Analysis of Outcome Measures

Summary statistics, including means, medians, and variances, will be calculated at each time point and for each type of data (e.g. parameters derived from index AF procedure and follow-up visits).

If patients withdraw from the study we will analyse data already collected, unless the patients request otherwise.

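### The four arms form a balanced 2x2 of RF power by target LSI, but sections 11.2-11.3 plan only a four-group comparison and summaries, with no power or LSI contrast, effect estimate or confidence interval

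*Combined protocol and SAP*

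**What the plan says.** Sections 8.2.3 and 9 define the arms as 20 W with LSI 4, 40 W with LSI 4, 20 W with LSI 5 and 40 W with LSI 5. Every power is paired with every LSI target. Section 8.2.3 puts 5 patients in each arm in each of four blocks of 20, so 80 patients give 20 per arm. The protocol does not use the word factorial, but the layout is a balanced 2x2.

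The first research question in section 3.4 is a power contrast: "is it better to use higher RF powers for shorter times, than lower RF powers for longer times", judged by oesophageal overheating and temperature alerts. The same section says "The rate of oesophageal alerts will be collected and compared for each procedure modality". Section 11.1 says the study "aims to give some insights about the relation among RF power, LSI and incidence of oesophageal temperature alerts" and that "it has been designed as pilot study for power analysis and sample size calculation of a further main study".

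For the analysis, section 11.2 states "Comparison of primary, secondary and tertiary outcome measures among different treatment groups will be performed at each time point using appropriate statistical testing", and then "ANOVA tests will be used to compare numerical variables and chi-square tests will be used to compare categorical values". Section 11.3 adds "Summary statistics, including means, medians, and variances, will be calculated at each time point and for each type of data". No section names a comparison of 20 W with 40 W, a comparison of LSI 4 with LSI 5, an interaction, an effect measure or a confidence interval.

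**The concern.** The design can estimate the power effect from all patients, 40 against 40, and the protocol's first question asks for that effect. The stated analysis instead asks whether four groups differ somewhere. For a yes/no alert that is a chi-square on 3 degrees of freedom, and its p-value does not say whether power, LSI or a particular combination is responsible.

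This matters because the pilot is meant to feed a sample size calculation. That calculation needs a chosen contrast, a plausible size for it and some view of its uncertainty. If the contrast is not fixed in advance, the one carried forward could be whichever looks largest among several. Such an estimate tends to be too large, and a main study sized on it too small.

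**Working it through.** **The plan's own figure.** Section 11.1 wants 12 patients per arm with primary outcome data and cites an alert rate of 55-75%. At 60%, 12/0.60 = 20 per arm, or 80 in total, which matches the plan. At 55%, 12/0.55 = 21.8, so 22 per arm and 88. At 75%, 12/0.75 = 16 per arm and 64. The plan does not name 60%, but it lies in the stated range. I use 20 per arm below. No alpha, power or effect size is stated.

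**Assumptions.** Alert is yes/no per patient; all 20 patients in each arm are ablated and counted; intervals are normal-approximation 95% intervals. The alert counts are illustrative.

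**Does the four-group test separate the factors?** Take three patterns with 52 alerts in 80 patients (65%). Each arm then has 13 expected alerts and 7 expected non-alerts, and every observed count is 3 away from expectation:

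chi-square = 4 x 9/13 + 4 x 9/7 = 2.77 + 5.14 = 7.91 on 3 df, p = 0.048.

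The sum of the four arm variances is 2 x (0.8 x 0.2 + 0.5 x 0.5)/20 = 0.041. A main effect has half-width 1.96 x sqrt(0.041)/2 = 0.198. The interaction, as a difference of differences, has half-width 1.96 x sqrt(0.041) = 0.397. Effects are in percentage points, 20 W minus 40 W and LSI 4 minus LSI 5:

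| Alerts of 20: 20W/LSI4, 40W/LSI4, 20W/LSI5, 40W/LSI5 | Power effect | LSI effect | Interaction | Four-group p |
|---|---|---|---|---|
| 16, 10, 16, 10 | 30 (10 to 50) | 0 (-20 to 20) | 0 (-40 to 40) | 0.048 |
| 16, 16, 10, 10 | 0 (-20 to 20) | 30 (10 to 50) | 0 (-40 to 40) | 0.048 |
| 16, 10, 10, 16 | 0 (-20 to 20) | 0 (-20 to 20) | 60 (20 to 100) | 0.048 |

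One p-value fits a pure power effect, a pure LSI effect and a pure interaction.

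**What the interval adds.** For the first row, size a main study of power setting (80% power, two-sided 5%, rates centred on 65%, no continuity correction). It needs 39 per group at the estimate of 30 points (80% v 50%), 356 at the lower limit of 10 points (70% v 60%) and 14 at the upper limit of 50 points (90% v 40%).

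**Precision over the protocol's 55-75% range.**
- Main effect, 40 v 40: 1.96 x sqrt(2p(1-p)/40) = 21.8 points at 55% and 19.0 at 75%.
- One pair of arms, 20 v 20: 1.96 x sqrt(2p(1-p)/20) = 30.8 points at 55% and 26.8 at 75%.
- Interaction: 1.96 x sqrt(4p(1-p)/20) = 41.8 points at 65%, and 43.6 to 38.0 over the range.

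**The case against.** The strongest reply is that nothing is lost. The arm summaries will be reported, and for a yes/no alert the four rates and their denominators determine every effect and interval above. That is correct: what is missing is pre-specification, not information. A reader might infer that the main study cannot be sized without this change, or that its size requires an interaction estimate. The documents support neither. The effects can be derived later, and a sample size needs a chosen contrast, a rate or SD and a target difference. What stands is that a contrast derived later can be chosen with the results in view.

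A second reply is that the protocol looks for the best combination of settings, which a four-group comparison suits. That holds for that question, and the comparison should stay. It does not answer the first question in section 3.4, which concerns power. A reader might also take section 3.4 to ask for LSI 4 against LSI 5 on alerts. It does not: its LSI question is whether a target of 5 can be reached before alerts end delivery. The case for an LSI effect on alerts rests on the general aim in section 11.1.

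Third, ANOVA may mean two-way ANOVA. The wording permits it, so the plan cannot be said to exclude a factorial model. But no factor terms are stated, and the reading does not help a chi-square on four groups.

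Fourth, the three patterns were built to share a p-value, and the spread of 14 to 356 reflects 20 patients per arm. Both points are fair. Factorial wording shows that imprecision but does not reduce it. Nor is a factorial analysis always the more sensitive: in the third pattern both main effects are zero.

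**Conclusion.** The point holds as a gap in pre-specification. The design is a balanced 2x2 and the protocol asks a power question, yet the stated analysis isolates no power effect and plans no estimate or interval to carry forward. That the four-group chi-square cannot separate the factors does not depend on the illustrative rates. The percentage-point figures do depend on a per-patient yes/no alert with 20 ablated patients per arm, and they would not apply to a rate per RF application.

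Main effects would be known to about 19 to 22 points either way, against 27 to 31 for a single pair of arms. The interaction would be known only to about 42 points at a 65% rate. In an 80-patient pilot with no confirmatory hypothesis, this is a minor to moderate improvement. The unstated unit of the alert rate (section 4) and the section 11.1 aim to recruit 80 "in order to achieve primary outcome data in 12 patients per group" are separate issues and add no weight here.

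**What to change.** In section 11.2, add a factorial analysis of the primary outcome in all ablated patients, including those with no alert, with terms for RF power and target LSI:
- numerical outcome: two-way ANOVA;
- yes/no alert: logistic regression or a stratified risk difference;
- count, or rate per RF application: a count model or a model clustered by patient.

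Report the power effect and the LSI effect, each with a 95% CI, beside all four arm results. Report the interaction with its 95% CI as descriptive only, neither a gate nor a requirement for the main-study size. Keep the four-group comparison for the best-combination question. All can be presented as estimates, with no test designated confirmatory.

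The cost is analysis wording, with no new patients, data or procedures. The downside is that each main effect averages over the other factor. Interaction is plausible here: section 3.2 describes LSI as non-linear in power, contact force and duration, and section 9 stops delivery at the temperature limit or at 60 seconds whatever the LSI. The main effects must therefore be read with the interaction and the four arms.

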4. OBJECTIVES AND OUTCOME MEASURES

Objectives	Outcome Measures	Timepoint(s) of evaluation of this outcome measure (if applicable)

Primary Objective
 
To compare the risk of oesophageal damage associated with different RF settings during AF ablation on the LA posterior wall
	
Rate of oesophageal temperature alerts (defined as oesophageal temperature rise > 39°C) during RF ablation on the LA posterior wall
	
Index procedure

Secondary Objectives
 
1. To compare the acute success of the index AF ablation using different RF settings on the LA posterior wall
 
2. To compare the short-term success of the index AF ablation using different RF settings on the LA posterior wall
 
3. To compare the rate of oesophageal injury related to different RF settings on the LA posterior wall during the index AF ablation
	
1. Rate of first-pass PVI, rate of acute PVR related to breakthrough signals on the LA posterior wall, total procedure time and RF ablation time
 
2. Freedom from atrial fibrillation
 
3. Rate of oesophageal symptoms (difficult or painful swallowing, heartburn, acid reflux, sore throat, hoarseness, cough, nausea, vomiting, non-cardiac chest pain)
	
1. Index procedure
 
2. During the follow-up period (6 months)
 
3. During the follow-up period (6 months)

Tertiary objectives
 
To evaluate the rate of complications associated with the different RF settings
	
Pericardial effusion, TIA/stroke, phrenic nerve injury, pulmonary vein stenosis, open-heart surgery, death
	
Index procedure

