8.2.3. Randomisation

A block randomization, with blocks of size four, type 1234, will be used to assign each patient to one of the following four treatment arms:

- ✓ Group 1: 20 W RF power and target LSI = 4 on LA posterior wall;
- ✓ Group 2: 40 W RF power and target LSI = 4 on LA posterior wall;
- ✓ Group 3: 20 W RF power and target LSI = 5 on LA posterior wall;
- ✓ Group 4: 40 W RF power and target LSI = 5 on LA posterior wall.

Briefly, the study population will be divided into 4 blocks of 20 patients. Within each block, every patient will be randomly assigned to 1 of the 4 treatment arms by using sealed envelopes. At the end of each block of 20 patients, there will be 5 patients enrolled in each of the 4 treatment arms. At the baseline visit, following consent, the study nurse or doctor will telephone the Research Office and ask the administrator to open a sealed envelope from the current block of 20 and reveal the allocated treatment arm. The treatment will be unblinded to the investigator and blinded to the patient.

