8.8. Definition of End of Study

The end of study will be the date of the last 6-month telephone follow-up.

9. INTERVENTION: AF ablation

As current practice in our centre, all AF ablations will be performed under general anaesthesia and on uninterrupted therapeutic anticoagulation with warfarin (target INR 2-3 in the last 3 weeks at least) or one of the new non-Vitamin K anticoagulant drugs. A heparin infusion will also be administered during the procedure, with target Activated Clotting Time (ACT) values of 300-350 sec. Fluoroscopy and tri-dimensional electroanatomical mapping will be used by the operator, as usual, as anatomical guide during the procedure.

The procedure critical steps can be detailed as follow:

- *General anaesthesia and TOE.* After general anaesthesia and oro-tracheal intubation, a trans-oesophageal echocardiogram (TOE) will be performed to rule out the presence of thrombus in the LA appendage.

- *Vascular access, coronary sinus catheter placement and LA access.* Venous femoral access will be achieved and a deflectable decapolar diagnostic catheter placed to the coronary sinus. One or two atrial trans-septal punctures will be performed under TOE-guidance. The choice of the trans-septal kit (needle and sheath) and of the number of performed trans-septal punctures will be left to the operator.

- *Luminal oesophageal temperature monitoring.* After the trans-septal puncture(s), the TOE probe will be taken out. A two-plane sinusoidal oesophageal temperature probe, CIRCA's S-Cath (CIRCA, Englewood, CO) will be placed orally to the oesophagus and advanced to the level of the LA. It will be connected to a dedicated CIRCA Temperature Monitor (CIRCA, Englewood, CO), displaying graphically and numerically temperature data from all 12 sensors, updated 20 times per second. Any luminal oesophageal temperature rise $\geq 39^{\circ}\text{C}$ will result in a temperature alert and cessation of RF delivery at that site.

- *LA geometry.* The LA geometry will be reconstructed using the EnSite Velocity mapping system (SJ Medical, St Paul, MN, USA) and an Optima mapping catheter (SJ Medical, St Paul, MN, USA).

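### The primary event is a fixed 39°C crossing, but each patient's pre-RF oesophageal temperature is neither stated to be recorded nor used in the comparison: a cheap precision gain, of unknown size, may be missed

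*Combined protocol and SAP*

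**What the plan says.** Section 4 defines the primary outcome as "Rate of oesophageal temperature alerts (defined as oesophageal temperature rise > 39°C) during RF ablation on the LA posterior wall". Although it is called a rise, this can only be an absolute level. Section 9 treats it the same way: reaching the level "will result in a temperature alert and cessation of RF delivery at that site". Section 4 writes > 39°C and section 9 writes ≥ 39°C. These must be reconciled, but under both the event is a fixed threshold and not a change from the patient's own start.

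In section 9 the temperature probe goes in after trans-septal puncture. LA geometry and ablation are listed after it. The monitor is described as "displaying graphically and numerically temperature data from all 12 sensors, updated 20 times per second". A pre-RF reading is therefore on display in every patient, but no section says that it is written down.

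Section 11.2 says that comparisons among treatment groups "will be performed at each time point using appropriate statistical testing", and then names the tests: "ANOVA tests will be used to compare numerical variables and chi-square tests will be used to compare categorical values". Sections 11.2 and 11.3 mention no covariate, and section 8.2.3 states no stratification factor. Allocation is equal: "At the end of each block of 20 patients, there will be 5 patients enrolled in each of the 4 treatment arms". With four such blocks, that is 20 patients per arm.

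**The concern.** The distance a patient has to travel to 39°C is part of what decides whether an alert occurs, and it is set before any randomised setting is applied. As an illustration, with values that are not from the documents, a patient at 37.0°C needs 39 − 37.0 = 2.0°C and one at 35.5°C needs 39 − 35.5 = 3.5°C. The starting temperature is the outcome variable itself, measured before treatment, so it is a natural candidate for adjustment.

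If it predicts alerts and is left out, variation that it could explain stays in the error of the primary comparison. Any chance difference in starting temperature between arms of 20 also goes uncorrected. If the value is never written down, no later analysis can use it, and the main study that this pilot is meant to inform cannot learn whether adjustment is worthwhile.

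**Working it through.** **1. The plan's own figure.** Section 11.1 states: "we aim to a final sample size of 12 patients with primary outcome data per each treatment group". It quotes an alert rate p of 55-75% and a total of 80. With N = 4 × ceil(12/p), rates of 55, 60, 65, 70 and 75% give 88, 80, 76, 72 and 64. The 80 is exact at 60%, inside the quoted range. It means 20 per arm, or 40 v 40 when arms are pooled by RF power.

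**2. Assumptions.** The documents give no SD of starting temperature, no correlation (rho) with the tendency to alert, no alpha and no effect size. I take two-sided 5%, a yes/no alert per patient, and a range of rho. To show what rho might mean: if peak = start + rise, with start and rise independent, rho = SD_start/√(SD_start² + SD_rise²). With an assumed SD_start of 0.5°C:
- SD_rise 0.8°C: 0.5/√(0.25 + 0.64) = 0.53
- SD_rise 1.5°C: 0.5/√(0.25 + 2.25) = 0.32

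**3. Is the unadjusted test valid?** In 20,000 simulated trials per scenario (4 × 20, 65% alerts in every arm, rho 0 to 0.7), the chi-square rejects a true null in 4.8-5.1%, both for the four-group test and by power group. In a separate simulation with 65% v 65% and rho 0.5, rejection is 4.8% (chi-square), 5.3% (unadjusted likelihood-ratio) and 5.4% (adjusted). Leaving out the covariate does not inflate the error rate.

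**4. How large is chance imbalance?** In SD units, the standard error of the difference in mean start is √(2/40) = 0.22 for 40 v 40 and √(2/20) = 0.32 for 20 v 20. At the assumed SD of 0.5°C these are 0.11°C and 0.16°C. The largest gap among four arms has a median of 0.44 SD and is at least 0.5 SD in 39% of trials. The two power groups differ by more than 0.4 SD in about 7% of trials. Within those trials, under a true null:

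| rho | chi-square rejects | adjusted test rejects | shift in alert rate when one group starts warmer |
|---|---|---|---|
| 0.2 | 5.9% | 5.2% | about 4 points |
| 0.3 | 7.4% | 5.8% | about 5 points |
| 0.5 | 11.8% | 5.5% | about 9 points |
| 0.7 | 17.4% | 4.9% | about 12 points |

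**5. How much precision is at stake?** For 75% v 55% (the ends of the range in section 11.1, used only as an example), 40 v 40, likelihood-ratio tests from logistic models without and with the starting value:

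| rho | unadjusted | adjusted | gain (points) |
|---|---|---|---|
| 0.1 | 48.6% | 49.1% | 0.5 |
| 0.2 | 46.8% | 47.8% | 1.0 |
| 0.3 | 46.7% | 49.2% | 2.5 |
| 0.5 | 49.6% | 55.1% | 5.5 |
| 0.6 | 47.8% | 57.9% | 10.1 |

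Unadjusted power does not depend on rho, so the spread in the second column is simulation noise. The rows for 0.3 to 0.6 used 4,000 runs, a standard error of √(0.5 × 0.5/4000) = 0.8 points for each power. Another run of this comparison gave 48% to 54% at 0.5 and gains of about 1 point or less at 0.1-0.3. The gain at 0.3 is therefore best stated as about 1-3 points.

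A second model (65% v 35% by power; planned chi-square against a linear risk-difference model with the starting value) gives:

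| rho | 40 v 40 | four-group test | variance ratio, unadjusted/adjusted |
|---|---|---|---|
| 0.2 | 79.9% to 78.9% | 60.7% to 62.2% | 1.01 |
| 0.3 | 79.2% to 79.4% | 60.2% to 63.2% | 1.04 |
| 0.5 | 79.6% to 84.3% | 60.1% to 68.7% | 1.16 |
| 0.7 | 79.2% to 90.2% | 59.8% to 77.8% | 1.41 |

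The two models agree: little or nothing up to about 0.3, and a worthwhile gain from about 0.5.

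**6. If the outcome is numerical (ANOVA).** Residual variance is multiplied by 1 − rho²: 0.96, 0.91, 0.75 and 0.51 at rho 0.2, 0.3, 0.5 and 0.7. A comparison with 50% power unadjusted would have Φ(1.96/√0.75 − 1.96) = Φ(0.30) = 62% at rho 0.5.

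**The case against.** The strongest reply is that nothing here is an error. An unadjusted comparison of randomised arms is valid, and the general wording of section 11.2 does not exclude a covariate. This is a pilot with no stated power or effect size, so power is an awkward yardstick. The 75% v 55% contrast borrows a range across earlier studies, and pooling to 40 v 40 is not the stated comparison among groups. Every gain rests on an assumed correlation, and at 0.2 or below there is essentially none. A 37.0 v 35.5°C contrast between two patients would be three SDs at an assumed SD of 0.5°C, far larger than any likely difference between arm means.

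Most of this stands. It limits the point to a possible gain in precision and does not remove it. The four-group results and variance ratios in the working do not depend on the pooling. An estimate with smaller variance is useful in a pilot too, and a covariate that general wording merely allows has not been pre-specified.

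A reader might infer more: that differences in starting temperature could pass for an effect of the settings, so that the primary comparison is biased. The documents do not support that. Arms are randomised, so such differences are chance and already covered by the 5% error rate. The marked case in the working arises in about 7% of trials. A reader might also infer that a recorded value is being ignored. Section 9 says only that temperatures are displayed.

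Two practical objections also stand and shape the fix. The reading would follow randomisation, in the hands of an unblinded investigator (sections 8.1 and 8.2.3). And section 9 does not state the order in which the walls are ablated, so a value taken before the first RF may predict posterior-wall alerts less well than one would hope.

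**Conclusion.** A cheap improvement, not a flaw in validity. The primary event is an absolute threshold, its pre-treatment value is on display in every patient, and the plan neither states that it is recorded nor uses it. The planned test keeps its type I error at about 5%. What may be lost is precision, and chance imbalance in the realised trial stays uncorrected.

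For 75% v 55% with 40 v 40, comparing like with like, the gain is about 0-1 point of power at a correlation of 0.1-0.2, about 1-3 at 0.3, about 6 at 0.5 and about 10 at 0.6. Which row applies cannot be told from the documents. The figures assume a yes/no alert per patient and a normally distributed latent tendency to alert. The plan does not define whether the unit is the patient or the RF application, so whether chi-square or ANOVA applies is open. Neither test as written uses the starting value.

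**What to change.** 1. **CRF.** Add one field: the maximum luminal temperature across the 12 sensors, read by a written procedure at a fixed moment before the first RF application at any site. The moment and method must be fixed in advance because the team already knows the allocation.
2. **Section 11.2.** Pre-specify this value as a continuous covariate in the primary comparison of alerts. Report an adjusted risk difference, for example standardised from a logistic model, so that the result stays comparable with raw alert proportions. Keep the unadjusted chi-square as supportive.
3. **Later readings.** State that temperatures before subsequent applications will not be used as covariates, since earlier RF at the allocated setting can warm them.
4. **Reporting.** Give the SD of the starting value and its association with alerts, so that the main study can decide on adjustment. This is useful even if the association proves weak.
5. **Wording.** State the unit of the primary outcome and reconcile > 39°C with ≥ 39°C.

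Cost: one number per patient from a monitor already in use, and one covariate. Patients already treated (Appendix C refers to the first 10 cases) may lack the value. Whether stored records exist is not stated, so the plan must say how missing values are handled. The gain is negligible if starting temperature varies little or predicts alerts weakly.

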6. STUDY RISKS AND BENEFITS

6.1. Study risks

The patients taking part will be undergoing a standard AF ablation on the basis of clinical reasons (symptoms and no response to medical therapy). When compared with the ablation protocol currently used in our centre, the study ablation protocol differs only for the use of predefined RF powers and target LSI values during PV encirclement on LA posterior wall. All proposed values of RF power and LSI have been already tested and approved in preclinical and clinical studies. Therefore no additional risks are expected from the study procedure.

Standard risks associated with an AF ablation procedure in our centre:

- bruising in the groin, mild chest discomfort, a sore throat and palpitations, which are usually self-limiting, occur in 1 in 10-20 people
- femoral vascular injury requiring a minor surgical repair occurs in 1 in 200 people;
- cardiac perforation requiring a drain at the time of the operation occurs in 1 in 50-100 people;
- pulmonary vein stenosis requiring treatment is 1 in 500;
- TIA or stroke is approximately 1 in 200 people;
- needing urgent open-heart surgery is 1 in 500 people;
- fatal complication is estimated to be 1 in 1000 people;
- cancer secondary to fluoroscopy exposure during the AF ablation is negligible considering the average low radiation dose and the short fluoroscopy time used.

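### Chi-square is the only test named for complications with an expected 0.02 to 0.4 events per arm, so a cluster of events would carry a misleading p-value

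*Combined protocol and SAP*

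**What the plan says.** Section 11.2 sets one rule for all outcomes: "Comparison of primary, secondary and tertiary outcome measures among different treatment groups will be performed at each time point using appropriate statistical testing". It then becomes specific: ANOVA for numerical variables, and "chi-square tests will be used to compare categorical values". It names no exact test, no minimum expected count and no descriptive-only option for rare events. Section 11.3 adds only summary statistics.

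The tertiary outcomes in section 4 are "Pericardial effusion, TIA/stroke, phrenic nerve injury, pulmonary vein stenosis, open-heart surgery, death". They are categorical, so chi-square is the named test for them.

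Section 6.1 gives the centre's own risk figures for several of these events. The most frequent is that "cardiac perforation requiring a drain at the time of the operation occurs in 1 in 50-100 people". Section 8.2.3 fixes the arm size: "the study population will be divided into 4 blocks of 20 patients", and "At the end of each block of 20 patients, there will be 5 patients enrolled in each of the 4 treatment arms".

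**The concern.** The Pearson chi-square p-value relies on a large-sample approximation that is usually trusted when expected counts are about 5 or more. The protocol's own risk figures put the complication tables far below that, and this could be seen when the plan was written.

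The study compares radiofrequency settings, and its results are meant to inform a main study. If a few complications fell in one arm, the planned test would return a p-value well below the exact one. A reader could take that as stronger evidence against a setting than the data give.

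**Working it through.** **Inputs**
- Total sample size 80 (section 11.1: "we plan to recruit a total of 80 patients in order to achieve primary outcome data in 12 patients per group").
- Four arms, and four blocks with 5 patients per arm in each (section 8.2.3).
- Complication rates from section 6.1.
- Alert rate for the primary outcome (section 11.1: "oesophageal temperature alerts occur in 55-75% of AF ablations").
- Alpha is not stated in the documents. I assume 0.05.

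**Arm size.** 4 blocks × 5 = 20 per arm, and 20 × 4 arms = 80, which matches the plan. Section 11.1 also fits: 12 patients with alerts per arm ÷ 0.60 = 20 per arm, and 60% lies inside the stated range.

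**Expected events per arm = 20 × rate**

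| Complication with a quoted rate | Rate | Expected per arm |
|---|---|---|
| Perforation needing a drain | 1/100 to 1/50 | 0.2 to 0.4 |
| TIA or stroke | 1/200 | 0.1 |
| Stenosis needing treatment | 1/500 | 0.04 |
| Urgent open-heart surgery | 1/500 | 0.04 |
| Death | 1/1000 | 0.02 |

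Added together at their highest, the rates are 2 + 0.5 + 0.2 + 0.2 + 0.1 = 3.0%, or 0.6 events per arm. An expected count of 5 per arm would need 20 events in 80 patients, a rate of 25%.

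**One table by hand: three events, all in one arm.** Expected per arm: 3/4 = 0.75 events and 19.25 non-events.
- Chi-square = (2.25² + 3 × 0.75²)/0.75 + (2.25² + 3 × 0.75²)/19.25 = 9.00 + 0.35 = 9.35 on 3 df, p = 0.025.
- Exact p = 4 × C(20,3)/C(80,3) = 4 × 1140/82160 = 0.0555.

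**Other tables, by full enumeration with 20 per arm**

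| Split over arms | Chi-square p | Exact p | Ratio |
|---|---|---|---|
| 1/0/0/0 | 0.386 | 1.000 | 0.39 |
| 2/0/0/0 | 0.104 | 0.241 | 0.43 |
| 1/1/0/0 | 0.562 | 1.000 | 0.56 |
| 3/0/0/0 | 0.0250 | 0.0555 | 0.45 |
| 2/1/0/0 | 0.283 | 0.611 | 0.46 |
| 1/1/1/0 | 0.792 | 1.000 | 0.79 |
| 4/0/0/0 | 0.0055 | 0.0123 | 0.45 |
| 2/2/0/0 | 0.240 | 0.322 | 0.74 |
| 4/1/0/0 | 0.0271 | 0.0509 | 0.53 |

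The ratio is 0.43 to 0.45 when two to four events all fall in one arm. It moves towards 1 as events spread out, and some tables with six or more events reverse (3/3/0/0: 0.090 against 0.076). Of the tables shown, two change sides of 0.05: 3/0/0/0 and 4/1/0/0.

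**How often this would happen with no arm difference.** No table with two or fewer events can reach chi-square p < 0.05. For a 3/0/0/0 split in any arm:
- At a 2% rate, P(exactly 3 events in 80) = 0.139, and 0.139 × 0.0555 = 0.8%.
- At a 1% rate, 0.0379 × 0.0555 = 0.2%.

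Over all tables with up to 14 events:

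| Event rate | P(chi-square p < 0.05) | P(chi-square p < 0.05 but exact p ≥ 0.05) |
|---|---|---|
| 1/50 | 0.95% | 0.85% |
| 1/100 | 0.23% | 0.22% |
| 1/200 | 0.04% | 0.04% |

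The test is significant in well under 5% of such trials. When it is, the exact test usually disagrees: 0.85/0.95 is about 90% at 1/50.

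**Primary outcome, analysed per patient.** At 75% alerts the smallest expected cell is 20 × 0.25 = 5. At 55% it is 20 × 0.45 = 9. The problem does not arise there.

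**The case against.** The strongest reply is that Freeman-Halton is not the only valid standard. It is conservative with few events, because the observed table's whole probability counts towards p. The mid-p version, which counts ties half, nearly matches chi-square: 0.0278 against 0.0250 for 3/0/0/0, and 0.0268 against 0.0271 for 4/1/0/0. Most of the factor of two is therefore discreteness. This stands as a limit on how wrong the chi-square value can be called. It does not rescue the plan, which names neither version and gives no reason to rely on the approximation at these counts.

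Second, a reader might infer that the plan inflates the false-positive rate. The figures do not support that. At the quoted rates chi-square is significant in under 1% of trials with no arm difference. Even given the event total, its size at 0.05 is at most about 5.8% for up to 14 events.

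Third, the affected outcomes are tertiary, the study is a pilot, and no decision rule depends on them. That stands and lowers the stakes.

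Fourth, section 11.2 speaks of appropriate testing in general, which might seem to allow an exact test. But it goes on to specify chi-square for categorical data. At best the choice is left until the data are seen.

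**Conclusion.** The concern holds within limits. Chi-square is the only test named for tables with 0.02 to 0.4 expected events per arm, where its approximation is unreliable. If two to four complications all fell in one arm, the reported p-value would be a little under half the exact one. A change in significance is rare: 0.85% of trials per outcome at a 2% rate and 0.22% at 1%, assuming alpha 0.05 and no arm difference. The harm is to the p-value reported if a cluster occurs.

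Three wider readings are not supported:
- That chi-square p-values are about half the exact ones throughout. The ratio depends on how the events are spread.
- That every complication type is shown to be this sparse. Section 6.1 gives no rate for phrenic nerve injury, for effusion not needing a drain or for stenosis not needing treatment, although section 4 lists effusion and stenosis without those limits.
- That the primary comparison is affected. Analysed per patient at 55 to 75% alerts, it is not.

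**What to change.** In section 11.2, state that Fisher's exact test (Freeman-Halton for the four-arm comparison) will be used for any table with an expected count below 5, including the tertiary complications. Add that each arm's count and rate will be reported with an exact 95% confidence interval. At these event numbers the intervals tell the reader more than any test.

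The cost is a sentence or two in the plan, with no new data, no extra patients and no change to procedures. The downside is that exact p-values are usually larger and more conservative, so a real cluster would need to be somewhat more extreme to reach a given threshold.
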